## **4 RECRUITMENT**

### ***4.1 Recruitment***

The primary source of participants for the RISE Study is the active patient population of the study sites and their usual referral sources. Participants will be recruited over a three year period. Recruitment techniques include notices placed on bulletin boards at the medical centers, newspaper and radio advertisements and public service announcements, and referral from colleagues. Prescreening of electronic and clinical medical records is strongly encouraged to reduce available screen failure rates. Selection is based solely on the participant's ability to meet the criteria stated in the protocol and his/her willingness to participate in the study. Site-specific recruitment strategies are developed by each local study team.

The performance of the clinical centers in recruiting and retaining eligible RISE participants will be monitored by the CoC and the Recruitment and Retention Committee. Monthly recruitment summaries will be issued throughout the recruitment and randomization period detailing the number of potential participants screened, number randomized, and reasons for ineligibility or of refusal to participate by clinical center. The reasons for ineligibility or refusal to participate

**CONFIDENTIAL**

will be compared among the clinical centers, and if large differences are found, explanations for these differences will be sought. If the randomization rate falls below the desired number of participants per month, data on reasons for ineligibility and refusal will be used to try to identify strategies that would increase the randomization rate. Site visits may be needed and assistance will be offered to clinical centers struggling with recruitment efforts.

## ***4.2 Description/Justification of the Target Study Population***

Preliminary screening will be done to enrich the yield of individuals who have prediabetes or type 2 diabetes. These individuals will be invited for initial field testing using HbA1c criteria. This testing will be performed on individuals who are highly predisposed to develop type 2 diabetes including, but not limited to, those with one or more of the following features:

- Known impaired glucose tolerance (IGT) and/or impaired fasting glucose (IFG)
- Overweight or obesity (BMI  $\geq 25 \text{ kg/m}^2$  ( $\geq 23 \text{ kg/m}^2$  in Asian Americans) but  $\leq 50 \text{ kg/m}^2$ )
- Age  $>45$  years
- First degree relative with type 2 diabetes
- Sedentary lifestyle
- Those with low HDL cholesterol or high triglycerides, hypertension (i.e., “the metabolic syndrome”)
- Certain racial and ethnic groups (e.g., Non-Hispanic Blacks, Hispanic/Latino Americans, Asian Americans and Pacific Islanders, and American Indians and Alaska Natives)
- Women who had gestational diabetes, or who have had a baby weighing 9 pounds or more at birth
- Women with polycystic ovary syndrome (PCOS)

The lifetime risk for type 2 diabetes among these groups is substantially higher than that seen in the general population. Further, the presence of more than one of these factors enhances the likelihood of development of type 2 diabetes to an even greater degree than does the presence of any single factor noted above. A recent evaluation of diabetes risk attempted to quantify the value of well known diabetes-associated risk factors [88].

The presence of risk factors/characteristics noted above will prompt screening these persons with a POC HbA1C; those who have a value of  $\leq 7.2\%$  will be asked to undergo a standard 75 gm OGTT along with a lab-based HPLC HbA1c. In this way, the proportion of subjects who will undergo an OGTT will be at high likelihood of having IGT or newly diagnosed type 2 diabetes by virtue of their risk status and elevated POC HbA1C. This approach is designed to increase the

yield of detecting IGT and type 2 diabetes while simultaneously maximizing the use of resources (both in terms of effort of personnel and use of testing supplies).

This strategy will yield individuals who will be identified as being at high risk for  $\beta$ -cell dysfunction (risk group plus POC HbA1C  $\leq 7.2\%$ ). Of those who undergo a 75 gram OGTT and the lab-based HPLC HbA1c, we project that approximately one-third of individuals will meet study enrollment criteria, i.e., will have a fasting plasma glucose 95-125 mg/dl *plus* a 2-hour glucose  $\geq 140$  mg/dl *plus* a laboratory-based HbA1c  $\leq 7.0\%$ . There is no upper limit for the 2-hour glucose on OGTT.

### **4.3 Informed Consent**

The informed consent process will be performed in a quiet setting prior to the initiation of any study procedures. The subject will be provided adequate time to read and understand the written consent and ask questions as necessary. If they choose, they may take additional time to discuss the study with family and/or physicians outside the clinic setting. Consent documents are not signed until volunteers demonstrate adequate understanding of all aspects of the study and consent process. A copy of the consent will be given to the subject. There will be two consent forms – one for the Screening stage and one for the Intervention stage. Model consent forms are provided in Appendix A. Written informed consent will be obtained prior to initiation of any study-related activities.

In the event that a significant protocol change occurs, the informed consent documents will be adjusted appropriately and sites will submit the revised documents to their Institutional Review Board (IRB) for approval. Local IRBs will determine whether it is necessary to re-consent participants.

Sites will submit to the CoC stamped IRB approval letters and current copies of all consent forms prior to study initiation, and annually thereafter. These records will be maintained by the CoC as a central archive.

### **4.4 Staged Screening and Randomization**

Screening for enrollment in RISE will be conducted in a stepwise manner involving completion of an initial screening encounter, an OGTT screening visit and a 3-week run-in period at the end of which baseline measurements, including the OGTT and hyperglycemic clamp, will be performed. Screening proceeds from least invasive, most easily obtained criteria to the most demanding procedures. Once a participant is determined to be ineligible, the screening process stops.

**CONFIDENTIAL**

The staged screening process is intended to accomplish the following:

- identify potentially eligible participants for RISE,
- verify eligibility of participants,
- accomplish the objectives of the informed consent process,
- complete a run-in period,
- establish a research cohort likely to complete the study and adhere to the medication schedule and the complex testing of  $\beta$ -cell function and related measures, and
- randomize participants into RISE.

Complete definitions and procedures are in the Manual of Procedures.

All steps below will be conducted if and only if the individual provides written informed consent for participation in RISE. If for any reason the participant wishes not to participate in any of the activities and experimental procedures outlined in the informed consent, the consent form will not be signed and no further data collection or biological testing will be conducted. If the participant agrees to participate in RISE, he/she will provide written documentation by signing the consent form. If for any reason the participant wishes to withdraw from the study at any time, there will be no pressure upon the participant to continue and withdrawal will be documented.

Staged screening and enrollment includes the following steps:

1. *Initial Contact:* This contact aims to identify individuals who are predisposed to develop type 2 diabetes by virtue of having one or more risk factors (Section 4.2). Potential participants are seen and given detailed information about RISE, including research interventions, randomization, masking, test procedures, risks and benefits, and the eligibility process. If they give oral and/or written consent, they are first interviewed and records are reviewed for personal and medical history. If they pass these completely noninvasive eligibility criteria, they will have a POC HbA1c measurement. Should their value be  $\leq 7.2\%$ , they will be invited to attend the clinic for a full screening visit where a complete history will be taken and lab tests performed.
2. *Screening:* If the participant meets initial inclusion criteria, he/she will return for a physical examination, full eligibility testing, and instruction in taking medication for the placebo run-in phase. A fasting 75 gram OGTT will be performed. In order to qualify for further consideration, the fasting glucose must be between 95-125 mg/dl and the 2-hour glucose must be  $\geq 140$  mg/dl and the laboratory-based HbA1c must be  $\leq 7.0\%$ .
3. *Run-in:* If the above criteria are met, the participant will be asked to undergo a 3-week run-in period. The run-in period (described in Section 3.4.1) allows staff to evaluate a patient's suitability for RISE. At the end of the run-in, clinic staff will assess the patient's

**CONFIDENTIAL**

adherence to medication taking, assess final eligibility criteria, and determine whether the patient should be randomized to RISE.

4. *Final screening visit and randomization:* If the participant is eligible, informed consent is obtained, baseline data are collected and the OGTT and hyperglycemic clamp are performed. If after completion of these studies the participant is willing to be randomized, the participant is randomly assigned to a treatment group.

If during the screening process the participant is deemed ineligible, but his/her condition changes during the recruitment period (e.g., the participant has uncontrolled hypertension that becomes adequately treated or an active infection that has resolved), he/she may be reconsidered for inclusion if he/she maintains eligibility for three months. Screening procedures are re-initiated and the participant must meet all eligibility criteria at the time of re-enrollment.

A minimal amount of data is recorded on participants who fail screening (such as age group, gender, race/ethnicity, diabetes duration) for purposes of comparing participants versus nonparticipants.

## 5 PATIENT MANAGEMENT

### 5.1 *Description of RISE Research Facility Treatment(s)*

Study treatment interventions are described in detail above (Section 3.4). Glucose management (including study medications) will be provided free of charge to RISE participants. In accordance with standards of care, HbA1c will be monitored every 3 months. Procedures to be followed for rising HbA1c levels are described in Section 7.4. Beyond the treatment of the glucose-aspect of prediabetes and diabetes care, the research study will not assume responsibility for the medical care of the participant. Non-glucose aspects of diabetes care (e.g., blood pressure, lipids, obstructive sleep apnea) and non-diabetes related medical problems will be referred to the participant's primary care provider. When a potential treatment could affect the study's outcome(s), the RISE physician may discuss the choices with the participant's primary care provider. RISE Study labs will be shared with the provider, with the participant's permission. For those participants who do not have a primary care provider, the study staff will help find appropriate medical care.

### 5.2 *Drug Distribution*

Study medications will be distributed directly to individual study centers. Individual centers will organize and maintain inventory, in cooperation with their investigational or research pharmacy. Sites will ensure that sufficient medication is always on hand to allow medication

**CONFIDENTIAL**

distribution for the next three month period. This includes medications required for the next 12 randomized enrollees (i.e., on average three initial distributions for each of the four treatment arms) plus all of the upcoming distributions to enrolled participants who will be returning within three months. Expiration dates of all medications will be double checked and documented on arrival at the study center and at the time of distribution to participants to ensure that the provided supplies will not expire during the current treatment interval.

Except for the placebos (metformin and liraglutide) distributed during the 3-week run-in period, medication will be dispensed to participants in 3-month quantities, and bottles/boxes/containers will be collected from participants at the quarterly visits to allow compliance assessment by pill counting or residual volume estimation for liquid medications. Subsequent treatment supplies will be provided with each quarterly visit.

Non-study medications will not be provided through the RISE study clinical centers.

### **5.3 *Adherence Measures***

Adherence will be documented, monitored, and addressed as part of participant care and management and to monitor whether procedures are being implemented and followed equivalently across all sites. Adherence refers to all study procedures – not only taking the prescribed amount of study drug, but also attending scheduled study visits and completing procedures at those visits. The goal is to maintain high levels of adherence in all participants and across all sites. Primary adherence measures will address visit attendance and completion of study procedures, medication adherence, and adherence to recommended home glucose monitoring. Medication adherence will be assessed on a quarterly basis, by pill counting or by residual volume estimation of insulin glargine and liraglutide. Participants will be instructed to bring all study medications (including empty bottles/vials/pens) to study visits.

#### **5.3.1 Placebo Run-in**

Metformin placebo compliance will be assessed by pill counting. Liraglutide placebo compliance will be assessed by residual volume assessment.

#### **5.3.2 Liraglutide**

Liraglutide will not be blinded in RISE. Liraglutide pens contain 3 ml, and the amount that each participant should use is readily calculated based on their study dosing during and after titration. The expected amount consumed will be calculated and compared to residual amounts in the currently active pen, and in any residual unused pens.

**CONFIDENTIAL**

### **5.3.3 Insulin**

Insulin will not be blinded in RISE. Insulin use will be prescribed to assigned participants only for the first 3 months of their participation. The projected volume consumed cannot be generalized, but will need to be calculated for each participant based on their recorded dosing titration and their final dosing. The dosing administration record will be used to assess compliance, and confirmed with a residual volume assessment as with liraglutide pens.

### **5.3.4 Metformin/Placebo**

Active or placebo metformin compliance will be assessed by counting of dispensed and returned tablets.

## **5.4 *Retention***

Retention refers to efforts to prevent participant dropout or withdrawal from the study. It is critically important to successfully engage and retain participation over the course of the trial. For purposes of sample size estimation, we have predicted withdrawal rates of 10% during the 15-months of primary data collection and have adjusted sample size to meet study requirements. However, lower rates of attrition are desirable.

The Study Coordinator at each site is primarily responsible for monitoring participant attrition and initiating team conferences for retention strategies or dropout recovery rates. Individual sites will develop strategies to enhance retention specific to their locale and specific population. Activities at both the national and local level will be coordinated to maximize retention and minimize attrition. Subjects missing scheduled visits will be contacted within 24 hours of the scheduled visit to reschedule and discuss strategies to improve compliance. If the site is unable to contact the subject, the site will send a certified letter to the participant to encourage continuation in the trial even if they no longer wish to take the study medication. At the local level, study staff will implement efforts to personalize the study (mailing out personal notes, birthday cards, etc.).

Attrition is monitored regularly by the CoC and the Recruitment and Retention Committee. An attempt is made to collect data on the reason for leaving the study in the case of a participant who withdraws. Assistance is offered to any site with a higher than average attrition rate. Sites will also be encouraged to share their ideas and experiences via regular communication and conference calls for Study Coordinators. The CoC will prepare monthly reports on visit completion, compliance with the RISE Study protocol and participants on inactive follow-up.

**CONFIDENTIAL**

## 6 DATA COLLECTION

### 6.1 Main Study Procedures

The timing of major study procedures during the different phases of the study is illustrated in Figure 1. Outcomes using hyperglycemic clamp procedures will be obtained at baseline, at the end of 12 months of treatment, and after a 3-month washout period (i.e., 15 months post randomization). Additional outcomes will be obtained from the OGTT concurrent with the hyperglycemic clamp procedures, and also at additional time points -- at 6 months on therapy, and at 9 months after stopping therapy (i.e., 21 months post randomization). Blood and urine samples for planned measures will be collected at these visits, along with extra blood and urine samples that will be stored for future analyses. Further details on these measures are provided below, and are summarized in Figure 1 above. All procedures and measures will be conducted by centrally trained and certified staff.

#### 6.1.1 Fasting Blood and Urine Samples

HbA1c will be measured and fasting blood and urine samples will be collected at each 3-monthly study visit. Aliquots of fasting blood and urine will be stored for subsequent measurement of biomarkers. A blood sample for DNA will be collected at randomization for subsequent genetic analysis should funding become available. Routine chemistries for safety (examples include complete blood count, liver function tests, pregnancy tests) will be done at screening and at six months.

#### 6.1.2 Oral Glucose Tolerance Test (OGTT)

Participants will come to the clinical research testing facility in the morning following a 10-12 hour overnight fast. They will drink 75 grams of an oral glucose solution (centrally provided from a single manufacturer) over  $\leq 5$  minutes. Blood samples will be obtained 10, 20, 30, 60, 90, 120, 150 and 180 min after the glucose ingestion. OGTT procedures will be performed at baseline, at 6 and 12 months on active treatment, and 3 and 9 months after stopping treatment, i.e., 15 and 21 months after randomization.

#### 6.1.3 Hyperglycemic Clamp

Hyperglycemic clamps (goal steady state glucose levels of 200 mg/dl and  $>450$  mg/dl) will be performed at baseline, 12 months post randomization while on active treatment, and 15 months post randomization (i.e., after 3 months of washout). Participants will return to the testing facility to undergo the clamp after a 10-12 hour overnight fast. The clamp will be performed on a day separate from the OGTT.

**CONFIDENTIAL**

The clamp procedure will incorporate 3 main sets of blood sampling for the planned outcome measures: first phase (0-10 minutes); second phase (100-120 minutes); and maximal stimulated responses (from 10 minutes before arginine until 10 minutes after arginine). To guide the clamp, a small volume of arterialized venous blood will be obtained at 5-min intervals throughout for clamp for measurement of plasma glucose concentration and titration of the dextrose infusion.

For the OGTT and clamp measures, participants will be asked to refrain from vigorous exercise and tobacco use for 24 hours before the baseline measures. Study medications will be withheld the morning of testing.

## ***6.2 Eligibility Screening Measurements***

Screening and run-in procedures are listed in Table 1.

*Prescreening (initial contact):* Prescreening for potential eligibility will be done using a single random capillary (fingerstick) blood sample for measurement of HbA1C with a POC instrument. Participants are eligible to continue screening procedures if the POC HbA1C is  $\leq 7.2\%$  and screening questionnaire that includes a focused medical history, anthropometric and blood pressure measures indicate that they meet initial eligibility criteria. Subjects who are discovered to have HbA1c  $>7.2\%$  will be excluded from participation and referred for formal diabetes assessment and treatment through their regular health care provider(s).

*Screening:* Participants who meet pre-screening eligibility criteria will present to the study center for formal screening to undergo a standard 2-hour 75 gram OGTT, with samples analyzed in the central laboratory. Only fasting and 2 hour post-load samples will be obtained (a laboratory-based HbA1c must be  $\leq 7.0\%$ , fasting glucose must be 95-125 mg/dl and 2 hour glucose must be  $\geq 140$  mg/dl for eligibility in RISE). Eligibility lab tests will also be performed, including electrolytes, TSH†(when clinically indicated), triglycerides, creatinine, ALT, hemoglobin, and pregnancy test.

*Placebo run-in:* Participants meeting eligibility criteria will be instructed to begin the 3-week placebo run-in. Participants who have  $<80\%$  adherence with study medications during this run-in phase will be withdrawn from the study and no further study procedures will be performed. Participants who are adherent with  $\geq 80\%$  of study medication during run-in will proceed to baseline study measurements. Participants will be asked demographic and medical history information.

Table 1: Data Collection During Screening and Run-In Procedures

STEP	TEST / PROCEDURE	COMMENTS
1) Pre-screening	Screening HbA1C (POC)	Continue screening if $\leq 7.2\%$
	Screening questionnaire	Initial review of eligibility
	Height, weight and BP	Initial screening for eligibility
2) Screening	HbA1c, 75 gram OGTT (central lab); glucose at 0 and 120 min	Eligibility HbA1c $\leq 7.0\%$ , fasting glucose 95-125 mg/dl; 2-h glucose $\geq 140$ mg/dl
	Eligibility labs*	Laboratory eligibility criteria
	Demographics, medical history, medications and physical examination	Eligibility evaluation
3) Run-in	Placebo dispensed	Initiate run-in
	Evaluate	Determine eligibility for randomization

\*Eligibility labs: electrolytes, TSH†, triglycerides, creatinine, ALT, hemoglobin

†TSH should be assessed as part of trial screening procedures in the following settings: 1) reported use of anti-thyroid medication, 2) reported use of thyroid hormone, 3) reported history of thyroid disease or 4) clinical suspicion of thyroid disease on history and physical.

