### **3.3.1 $\beta$ -cell Function and Glucose Tolerance**

- (i) Hyperglycemic clamp-derived  $\beta$ -cell measures:
  - a. First phase insulin response (incremental insulin area from 0-10 minutes after initial glucose bolus)
  - b. First phase C-peptide response (incremental C-peptide area from 0-10 minutes after initial glucose bolus)
  - c. Disposition index derived from a and b, adjusting for insulin sensitivity using the hyperglycemic clamp-derived measure of insulin sensitivity (glucose disposal rate/insulin: GDR/I)
  - d. Second phase insulin response, with adjustment for insulin sensitivity using non-clamp-derived surrogate measures
  - e. AIRmax response to arginine calculated using insulin concentrations and adjusted for insulin sensitivity
- (ii) OGTT-derived  $\beta$ -cell measures:
  - a. Early insulin response to oral glucose (insulinogenic index:  $\Delta$  insulin from 0-30 minutes/ $\Delta$  glucose from 0-30 minutes [ $\Delta$ I/ $\Delta$ G])
  - b. Early C-peptide response to oral glucose (parallel to (a))
  - c. Oral disposition index (Dlo; insulinogenic index adjusted for insulin sensitivity)
  - d. Modeled parameters of  $\beta$ -cell function ( $\beta$ -cell glucose sensitivity, rate sensitivity and potentiation factor; static, dynamic, and total  $\beta$ -cell glucose sensitivity)
  - e. Ratios of incremental insulin/glucose (iAUCins/iAUCg) and C-peptide/glucose (iAUCc-p/iAUCg) responses from 0-120 minutes
  - f. Incremental glucose (iAUCg) response as a measure of glucose tolerance
  - g. 2-hour glucose
  - h. GLP-1 total and incremental response to oral glucose load (samples will be collected, and measured for this analysis if funding allows)
- (iii) Fasting measures:
  - a. Glucose
  - b. Proinsulin/insulin ratio
  - c. HOMA %B (using the Oxford calculator)
  - d. HbA1c

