**CONFIDENTIAL**

interest at the end of the intervention phase (12-months) and at 3-months and 9-months post-washout. As for the primary outcomes, all analyses will be adjusted for the baseline value of each outcome and will use the closed testing procedure described above to preserve an overall  $\alpha=0.05$  for those outcomes as well.

An important secondary analysis of this study is to determine whether  $\beta$ - and  $\alpha$ -cell function from OGTT and fasting samples are sufficiently well correlated with more robust assessments of  $\beta$ - and  $\alpha$ -cell function obtained from the hyperglycemic clamp to validate their use in large clinical trials. For these analyses, Pearson and non-parametric Spearman correlations of simple versus sophisticated measures of  $\beta$ - and  $\alpha$ -cell function will be computed. Correlations will be assessed for measures made both on and off therapy.

Finally, to examine biomarker associations with glucose metabolism, Pearson and non-parametric Spearman correlations of each biomarker with  $\beta$ - and  $\alpha$ -cell function, insulin sensitivity and glucose tolerance measures will be determined. In addition, multiple linear regression models will be developed to predict measures of glucose metabolism with the most informative biomarker sets.

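### Fasting and 2-hour glucose are measured twice before randomization, but Section 9.2 adjusts for one baseline value; adding the screening value is a valid, nearly free and modest gain in precision

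*Protocol*

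**What the plan says.** **Screening.** Protocol 6.2 has participants "undergo a standard 2-hour 75 gram OGTT, with samples analyzed in the central laboratory". It limits the draw: "Only fasting and 2 hour post-load samples will be obtained". Section 4.4 (step 2) uses these values for eligibility: "the fasting glucose must be between 95-125 mg/dl and the 2-hour glucose must be" at least 140 mg/dl, with a laboratory HbA1c of at most 7.0%.

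**Baseline.** Section 4.4 then describes "a 3-week run-in period at the end of which baseline measurements, including the OGTT and hyperglycemic clamp, will be performed". Its step 4 places this testing before random assignment. It is a separate test: Section 6.1.2 samples the outcome OGTT through 180 minutes, while Table 1 lists screening glucose at 0 and 120 minutes only.

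**Outcomes.** Section 3.3.1 lists "2-hour glucose" among the OGTT-derived measures, and glucose and HbA1c under "Fasting measures".

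**Analysis.** Section 9.2 compares secondary outcomes by ANCOVA at the end of treatment and at 3 and 9 months after it, and states that "all analyses will be adjusted for the baseline value of each outcome". Neither document uses the screening value as a covariate or averages it with baseline. The SAP covers only the clamp-based primary outcomes.

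**The concern.** A single OGTT value measures a person's usual glucose level with error, so adjusting for it removes only part of the between-person variation at follow-up. A second untreated value, taken about three weeks earlier with only placebo in between, carries further information on the same quantity. It must exist for everyone randomized, because eligibility depends on it. As written, the plan uses it for eligibility and then sets it aside.

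At stake is some precision in the glucose-tolerance comparisons at Months 12, 15 and 21, with 56 evaluable participants per arm. Section 9.2 also puts these outcomes through the closed procedure, where a pairwise test must first pass the four-group test and both relevant three-group tests. Lower residual variance helps at every step.

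**Working it through.** **1. The plan's own figures.** The documents give no figure for a second baseline value, so the check starts from Table 3 (56 per arm, two-sided 0.05, closed test). Simulating the closed test with one arm differing from the other three gives 82.6%, 85.5% and 78.1%, against the stated 81% (adjusted effect 0.60), 84% (0.62) and 77% (0.57). Recruitment: 224/0.9 = 249, against 255 planned. The stated design is reproduced closely.

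**2. Inputs for the gain.**
- Baseline to follow-up correlation ρ: Section 9.3 gives 0.57, for the primary clamp outcomes. No value is given for glucose, so using 0.57 here is an assumption.
- Screening to baseline correlation r: not given. Range used: 0.5 to 0.9.
- Selection: screening values are cut by eligibility (fasting 95-125 mg/dl, 2-hour at least 140 mg/dl). How far this narrows their range is not given.

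**3. Closed form, ignoring selection.** With one baseline value the residual variance is 1 − ρ². With two exchangeable values it is 1 − 2ρ²/(1 + r). At ρ = 0.57:
- one value: 1 − 0.3249 = 0.675
- r = 0.70: 1 − 0.6498/1.70 = 0.618, a cut of 8.5%
- r = 0.80: 1 − 0.6498/1.80 = 0.639, a cut of 5.3%
- r = 0.90: 1 − 0.6498/1.90 = 0.658, a cut of 2.5%

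**4. With selection, correlations set before selection.** Values were truncated at the eligibility limits. Assumed screened population: fasting mean 105, SD 12-15; 2-hour mean 140-150, SD 40-45; ρ 0.50-0.70; r 0.50-0.80. The cut is about 3-7%.

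**5. With selection, 0.57 imposed among those enrolled.** Screening value = true value + error, baseline value = true value + independent error of the same size, selection on the screening value. The last column is the correlation, among those selected, between baseline and an immediate repeat with the same error.

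| r | Cut, top third selected | Cut, 30th-90th percentile window | Baseline vs equally noisy repeat (top third / window) |
|---|---|---|---|
| 0.5 | 11.0% | 10.0% | 0.39 / 0.38 |
| 0.6 | 10.5% | 9.7% | 0.46 / 0.45 |
| 0.7 | 9.6% | 9.3% | 0.54 / 0.52 |
| 0.8 | 8.3% | 8.3% | above 0.57 |
| 0.9 | 5.7% | 6.0% | above 0.57 |

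The first three rows are not coherent. They need a follow-up value 12 to 21 months later to correlate with baseline (0.57) better than an immediate repeat would. At r = 0.5 the measured follow-up would have to correlate 0.91 with the true value, so it would be almost free of error. Only r of about 0.8-0.9 fits, giving about 6-8%.

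**6. Same model, follow-up with the same error as baseline.** If the true value at follow-up correlates 0.8 with the true value at baseline (assumed), the top-third cuts are 2.3%, 3.0%, 3.7%, 4.0% and 4.0% for r = 0.5 to 0.9. At a true-value correlation of 0.6 they are 1-2%.

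**7. What this is worth.** A cut of 1-8% narrows intervals by 1 − √0.99 = 0.5% to 1 − √0.92 = 4.1%. It equals 56/0.99 = 56.6 to 56/0.92 = 60.9 participants per arm, so about 1 to 5 more. For scale, a lone pairwise test at effect 0.60 has 88.8% power. A 3% cut gives 89.7% and a 6% cut gives 90.6%.

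**The case against.** The strongest reply is that nothing is wrong. Adjusting every outcome for its own baseline value is conventional and unbiased, and it keeps the rule uniform across a long list of outcomes. No secondary outcome is powered, and no conclusion, error rate or primary analysis depends on this choice. All of that stands, and it is why the point is a refinement.

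A reader might go further in four ways that the documents do not support:

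- **That the plan gives up something like 6-11% of residual variance.** The upper part of that range needs the incoherent combinations in step 5, and the 0.57 behind it belongs to the clamp outcomes.
- **That the least repeatable measure gains most.** Low repeatability also lowers the correlation with follow-up. In step 6 the gain is smallest at r = 0.5.
- **That 2-hour glucose is cut at its upper third.** Section 4.2 does say "we project that approximately one-third of individuals will meet study enrollment criteria", but that is the joint yield of the fasting, 2-hour and HbA1c criteria. The top-third case in the working is only an illustration.
- **That the primary comparison suffers.** Screening draws no insulin or C-peptide and includes no clamp, so there is no second value of either co-primary outcome or of any insulin- or C-peptide-based measure.

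In the other direction, eligibility truncation does not make the screening value unusable. It weakens the information the value adds, but selecting on a pre-randomization covariate does not bias an arm comparison adjusted for it.

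**Conclusion.** The point holds as a minor efficiency suggestion. The documents establish two pre-randomization values of fasting and 2-hour glucose, both as secondary outcomes, and an ANCOVA that names one baseline value. Adding the screening value is valid because treatment cannot have affected it.

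The size is modest: roughly a 1-8% cut in residual variance, most plausibly a few percent. The low end assumes follow-up glucose is measured with the same error as baseline and that true values correlate 0.6-0.8 over the interval. The high end assumes that 0.57 applies to glucose among those enrolled and that r is about 0.8-0.9. If glucose tracked more closely over time than this, the gain would be larger; the documents do not say. For HbA1c, an assumed r of 0.9 with only a mild upper cut gives about 3%.

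**What to change.** Add one sentence to Section 9.2: for fasting glucose and 2-hour glucose, and for HbA1c where it is repeated at baseline, the ANCOVAs at Months 12, 15 and 21 include the screening value as a second covariate alongside the baseline value. Apply it at every step of the closed procedure. All other outcomes keep their single baseline value.

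The screening to baseline correlation can be computed from blinded data to show what to expect. The sentence should be fixed before unblinding, so that the choice of covariates cannot look data-driven.

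Cost: one line of text and one degree of freedom per model. No new visits, samples or assays are needed.
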